**Exploratory Aim.** To evaluate the effect of varenicline on negative affect, and the relationship between negative affect and cannabis use reduction, during CUD treatment. **Exploratory Hypothesis 1:** A 12-week treatment course of varenicline, compared to placebo, for CUD will yield reduction in negative affect. **Exploratory Hypothesis 2:** Reduction in negative affect during varenicline treatment will be associated with cannabis use reduction.

**Participants.** A total of approximately180 participants with CUD, aged 18 and over, will be recruited over a 32-month period at 2 participating sites.

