Treatment Assignment. Individuals who meet all inclusion criteria and no exclusion criteria will be randomized to receive either varenicline or matching placebo. Randomization (stratified on tobacco smoking status and gender) and dispensing will be performed by the MUSC Investigational Drug Service. Varenicline will be provided at the standard recommended dose of 0.5mg daily for three days, then 0.5mg twice daily for four days, and then 1mg twice daily for the remainder of the 12-week treatment period. Matching placebo and varenicline (0.5mg and 1mg) capsules will be compounded by IDS utilizing Letco 00 capsules and microcrystalline cellulose filler. For the Pickens site, medication will be packaged and dispensed by MUSC IDS, and then shipped to Pickens via registered courier. On site, medication will be stored in a controlled access environment and provided to participants by appropriately trained and designated study staff, with double checks in place. In extenuating or emergency circumstances, when patient visits are not feasible or are prohibited, such as in the case of a pandemic, weekly medication may be mailed to participants.

Medication Management. Medication Management (MM) is a common-sense, generalizable approach to encourage adherence to medication specifically, and to a treatment plan in general. Once a week, participants will be seen for a brief MM session. Sessions will be focused on (a) developing and maintaining rapport, (b) reviewing AEs and concomitant medications, and (c) discussing progress with medication adherence and cannabis reduction/abstinence. These sessions provide an opportunity to address challenges and help participants devise strategies for success. A similar intervention was utilized in the NIDA-funded CTN0053 trial (Achieving Cannabis Cessation—Evaluating N-Acetylcysteine Treatment) to provide an evidence-based treatment platform for all participants. MM with participants at the Pickens site will be done by approved medical personnel there and, as needed, by MUSC site medical personnel via WebEx or Doxy.me, HIPAA-compliant, MUSC Information Security-approved platforms for telehealth. In extenuating or emergency circumstances, when patient visits are not feasible, safe, or are prohibited, such as in the case of a pandemic, MM at both sites may be completed remotely by telehealth/phone.

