impact on parameter inference, thus when detected, a negative binomial distribution will be specified and model fit will be compared to the Poisson model. An offset variable will be included in the models to account for possible differences in between visit timing. Models will be computed both adjusted for design variables and for significant covariates and confounders found in the preliminary analysis. Working correlation structures will be independently compared using the quasi-likelihood under the independence model criterion statistic (QIC). Model based means will be used to construct the pairwise comparisons between groups. All design adjusted models will include baseline average use sessions, study visit, treatment group assignment and randomization stratification variables (smoking status and gender). Additional exploratory approaches (e.g., analysis excluding participants with <80% medication adherence, per protocol analysis, completers analysis) will be undertaken.

**Specific Aim 2:** We will also compare the frequency of treatment-emergent AEs between treatment groups using a non-inferiority analysis. Of particular interest will be AEs leading to medication discontinuation and the occurrence of treatment-related serious AEs (SAEs). We will specifically compare neuropsychiatric AEs and suicidality (C-SSRS) ratings by treatment group. We hypothesize that treatment with varenicline will not cause undue adverse events and will be non-inferior to the placebo group by a margin ( $\delta$ ) of no more than a 10% using the Farrington-Manning score test for non-inferiority.

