### ***b. Sources of Materials***

Research material obtained from individual participants includes questionnaires and in-person and remote interviews with study personnel, and blood and urine samples. To ensure confidentiality, all participant data will be letter/number coded, and only the investigators will have access to the master lists of codes. The research material will be obtained specifically for research purposes. Written research material obtained will be stored in the Addiction Sciences Division at MUSC or at Behavioral Health Services of Pickens County in Pickens, SC, in an office that is locked when not in use. Urine samples from MUSC site will be stored in the Clinical Neurobiology

Urine samples from the Pickens site will be stored at Behavioral Health Services of Pickens County and then sent to MUSC CNL for analysis in batches.

*c. Potential Risks*

The varenicline package insert details adverse events associated with the medication. Specifically, it reports that "the most common adverse reactions (>5% and twice the rate seen in placebo-treated patients) were nausea, abnormal (e.g., vivid, unusual, or strange) dreams, constipation, flatulence, and vomiting." Meta-analyses of the four main adverse events in varenicline versus placebo groups in adult trials yielded relative risks (RRs) of 3.21 (95% CI 2.71, 3.80) for nausea, 1.50 (95% CI 1.26, 1.79) for insomnia, 2.79 (95% CI 2.09, 3.72) for abnormal dreams, and 1.20 (95% CI 1.00, 1.45) for headache (Cahill et al., 2009). While post-marketing anecdotal reports of psychiatric adverse events led to an FDA "black box" warning for varenicline, a reanalysis of controlled trials revealed no evidence that varenicline is associated with neuropsychiatric adverse events (Thomas et al., 2015). There is a potential risk of loss of confidentiality.

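### Site is neither a randomisation stratum nor a term in the design-adjusted models of this two-site trial; pre-specifying it would be a small gain in precision at almost no cost

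*Combined protocol and SAP*

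**What the plan says.** Study Overview and Design says that participants "will be recruited over a 32-month period at 2 participating sites". Under Procedures, Treatment Assignment: "Randomization (stratified on tobacco smoking status and gender) and dispensing will be performed by the MUSC Investigational Drug Service". Site is not a stratum.

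The sites differ in setting and staff. One is an academic medical centre; the other is a county behavioural health service (Sources of Materials). Under Medication Management: "MM with participants at the Pickens site will be done by approved medical personnel there and, as needed, by MUSC site medical personnel via WebEx".

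Statistical Analysis, Primary Analysis, Specific Aim 1, fixes the terms of the primary model: "All design adjusted models will include baseline average use sessions, study visit, treatment group assignment and randomization stratification variables". The two variables are then named in brackets as smoking status and gender. A second set of models is also adjusted for covariates. Under Baseline Analysis, these are characteristics that prove to be statistically related to the cannabis outcomes; site is not named there. The moderators listed under Additional Data Analysis are adherence, smoking status and gender. Missing Data and Attrition specifies the imputation method and 100 imputed files, but lists no imputation variables.

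**The concern.** Site is known for every participant before randomisation. Here it marks a difference in who delivers the behavioural platform that both arms receive, and in what setting. That could plausibly affect use sessions or retention.

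The design does not balance arms within site, and the design-adjusted model has no site term. Two things follow. First, any site difference in outcome not already explained by baseline use, smoking status or gender remains in the residual variance. Second, if the arms happen to differ in site mix, the treatment estimate is not corrected for it. The only route left for site is a screen on outcome data. That route does not reach the design-adjusted models, and it leaves open whether a later site adjustment was chosen after seeing results.

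**Working it through.** **Inputs from the documents.** Two sites; about 90 randomised per arm (180 in total); 57 evaluable per arm (114 in total); d = 0.5; correlation 0.95; 5% type 1 error; 80% power; 35% attrition; weeks 6-12, taken as 7 weekly measures.

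**Assumed, because the documents do not give them.** Share p at the smaller site: 20% to 50%. Residual site effect e, net of the planned covariates: 0.2 to 0.6 SD. Two-sided testing, since sidedness is not stated for efficacy. The arithmetic is Gaussian, whereas the planned model is Poisson or negative binomial with a log link.

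**1. The plan's own figure.** n = 2 × ((1.96 + 0.842)/0.5)² = 62.8 per arm for a single measure. The correlation structure is not stated. With first-order autoregressive correlation of 0.95, the mean of 7 measures has relative variance 0.893, and 62.8 × 0.893 = 56.0; the unrounded value is just above 56, giving 57 with power 0.807. Compound symmetry gives 0.957 and 61. Inflating for attrition, 57/0.65 = 87.7, or 88, against the stated 90 or so. The stated size therefore reproduces under the autoregressive reading.

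**2. Chance imbalance in site share.** SD of the between-arm difference = √(2p(1−p)/90).
- p = 0.2: √(0.32/90) = 0.060
- p = 0.5: √(0.50/90) = 0.075

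**3. Shift in the estimate, and participants recovered by adjusting.** A 2-SD imbalance shifts the estimate by 2 × SD × e. The variance explained by site is R² = p(1−p)e², and the equivalent number of participants is N × R²/(1−R²). Ranges run from p = 0.2 to p = 0.5.

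| e (SD) | 2-SD shift (SD) | Share of d = 0.5 | R² | Worth, N = 114 | Worth, N = 180 |
|---|---|---|---|---|---|
| 0.2 | 0.024 to 0.030 | 5% to 6% | 0.006 to 0.010 | 0.7 to 1.2 | 1.2 to 1.8 |
| 0.4 | 0.048 to 0.060 | 10% to 12% | 0.026 to 0.040 | 3.0 to 4.8 | 4.7 to 7.5 |
| 0.6 | 0.072 to 0.089 | 14% to 18% | 0.058 to 0.090 | 7.0 to 11.3 | 11.0 to 17.8 |

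A 2-SD imbalance or larger arises in about 5% of trials. A 1-SD imbalance gives half these shifts: 0.024 to 0.030 SD at e = 0.4.

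**4. Power at 57 per arm.** Without a site term the variance is inflated by 1 + p(1−p)e²/0.893. With the term, power is 0.807.
- e = 0.2: inflation 1.007 to 1.011, power 0.804 to 0.802.
- e = 0.5: inflation 1.045 to 1.070, power 0.789 to 0.780. At a 10% site share it is 0.797, so the loss is about 1 to 3 points across shares of 10% to 50%.

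**5. Simulation check** (6,000 runs per setting, 57 per arm). Power without versus with the term at e = 0.5 was 0.789 versus 0.804 at p = 0.2, and 0.765 versus 0.792 at p = 0.5. Type I error without the term, over all settings run, was 0.049 to 0.052.

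**The case against.** **The model already removes part of any site difference.** Baseline use, smoking status and gender are adjusted for, so whatever separates the sites through those variables is absorbed. This stands, and it is why the site effects above are defined as residual. It would be wrong to say that nothing in the plan deals with site differences.

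**Randomisation protects the comparison.** Chance imbalance in an unadjusted prognostic factor is already reflected in the standard error, and the simulated type I error is at its nominal level. This stands. A reader might infer that the primary comparison is biased; the documents do not support that.

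**The sites may hardly differ for this outcome.** The primary outcome comes from daily REDCap logs completed on the participant's own device. Both sites' drug comes from the same pharmacy: "For the Pickens site, medication will be packaged and dispensed by MUSC IDS, and then shipped to Pickens via registered courier". Batched urine testing is not the source of the primary outcome. Weekly Medication Management is planned at both sites. This mostly stands: courier and urine handling are no reason to expect a site effect on use sessions. What remains is the difference in local staff and setting, and the documents give no evidence either way on how much it matters.

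**The covariate-adjusted models could pick site up.** If site were put through the screen, the chance of detection with N = 180 at two-sided 0.05 is roughly Φ(e/SE − 1.96). SE is √(1/36 + 1/144) = 0.186 at p = 0.2 and √(2/90) = 0.149 at p = 0.5. That gives 57% to 77% at e = 0.4 and 90% to 98% at e = 0.6, so the screen would often find a site effect large enough to matter. But site is not named as a candidate, entry would depend on the outcome data, and the design-adjusted models would still lack the term.

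**Conclusion.** The omission is confirmed: site is not a stratum, a design-adjusted term, a named covariate or a moderator. The consequence is small. Unexplained site variation stays as noise, and a chance site imbalance is left uncorrected. The size rests on the assumed site shares and residual effects and on a Gaussian approximation. Within those limits it runs from negligible at 0.2 SD to a few participants' worth of precision at 0.4 SD and 1 to 3 points of power at 0.5 SD.

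Two further readings are tempting and should not be drawn. The sample size is not made wrong: 57 per arm reproduces, under the stated correlation and an autoregressive structure, without reference to site. Nor can it be said that the imputation model leaves site out, because the plan lists no imputation variables at all; the fair statement is that site is not specified there.

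This is a low-severity point, worth making because the remedy costs almost nothing.

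**What to change.** Add site as a pre-specified fixed effect to the design-adjusted primary model and to the abstinence and other secondary models. Name it among the variables in the imputation model. Keep it in whatever the significance screen shows, so that adjustment for site does not depend on outcome data.

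Randomisation need not change, and no new data or procedures are needed. The cost is one line in the analysis plan and one degree of freedom per model, from about 180 participants. If the sites turn out alike, almost nothing is lost.

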substance use report logs. We anticipate the increased information will allow better precision in the estimated effect between randomized study groups. Assuming this, coupled with the more extended 12-week treatment compared with the truncated treatment phase in the prior UG3 proof-of-concept trial, results in a slightly increased effect size of  $d=0.5$ , a high correlation between measures taken over time on the same participant ( $p=0.95$ ) and a 5% type 1 error rate, 57 participants are necessary in each treatment arm to achieve adequate power (80%). Additionally, the UG3 noted a higher than expected attrition rate of 35%, thus we anticipate that, despite our best efforts and revised approach, attrition during the study could reach 35%. Thus to ensure that we have the appropriate sample, we will enroll and randomize **approximately 90 participants per group for a total sample size of approximately n=180**. This will allow us to detect a difference in cannabis use session of at *least*  $d=0.5$  between randomized study groups while accounting for up to 35% study attrition. Similar to adult varenicline phase III studies (Gonzales et al., 2006), for the primary safety analysis we will compare the frequency of all treatment-emergent AEs (defined as any AE occurring between treatment initiation and one week following treatment conclusion), SAE's between varenicline and placebo groups. A non-inferiority analysis will be utilized (Piaggio et al., 2006). With an estimated placebo treatment-emergent AE rate of 75% (Gonzales et al., 2006), 90% power and two sided  $\alpha = 0.05$ , within our proposed sample of **approximately 180 randomized participants** we will be able to detect a 10% non-inferiority margin in AE frequency between treatment groups if it exists.

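### The Aim 2 adverse event non-inferiority test is named without the randomisation strata; stratifying it is a small, free gain in precision if adverse event risk differs by smoking status or gender

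*Combined protocol and SAP*

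**What the plan says.** Under Procedures, Treatment Assignment, the protocol specifies "Randomization (stratified on tobacco smoking status and gender"; no block size or other method of balancing within strata is given.

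In the Statistical Analysis section, the Specific Aim 1 text requires every design-adjusted efficacy model to contain "treatment group assignment and randomization stratification variables (smoking status and gender". The Specific Aim 2 text sets a 10% margin for treatment-emergent AEs, to be tested "using the Farrington-Manning score test for non-inferiority". It neither calls the test unstratified nor describes a stratified version.

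Power and Sample Size calls this the primary safety analysis. It gives an "estimated placebo treatment-emergent AE rate of 75" per cent, "90% power and two sided" alpha of 0.05, and a sample of "approximately 90 participants per group for a total sample size of approximately n=180", and concludes that "we will be able to detect a 10% non-inferiority margin in AE frequency between treatment groups if it exists". The varenicline AE rate is not stated, and no AE rate by smoking status or gender appears anywhere.

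**The concern.** A Farrington-Manning test, named without qualification, compares two simple proportions. Its variance is built from the overall proportion in each arm and so includes variation between strata. When randomisation balances the arms within strata, that variation cannot contribute to a chance difference between the arms. The test then uses a standard error somewhat larger than the true one. Its confidence limit sits too far out, its real level falls below nominal, and it fails slightly more often when varenicline truly is non-inferior.

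Non-inferiority is decided by a single confidence limit, and the efficacy analysis already uses the strata. Leaving them out of the safety test gives away precision that the design may already have provided. It also leaves open which limit decides a borderline result.

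**Working it through.** **Inputs from the documents.** Placebo AE rate 75%; margin 10%, read as 10 percentage points; two-sided alpha 0.05, so one-sided 0.025; 90 per arm.

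**Assumptions.** Varenicline AE rate 75% (no true difference); strata of equal size; arms balanced within strata. Stratum AE rates are assumed and shown as a range.

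**1. The plan's own power figure.** Variance of the risk difference: 2 × 0.75 × 0.25 / 90 = 0.004167, so SE = 0.0645. Power = Φ(0.10/0.0645 − 1.96) = Φ(−0.41) = 34% (33.9% with the Farrington-Manning null variance). One-sided 0.05 gives 46%. The stated 90% is not reproduced. It would need 2 × 0.1875 × (1.960 + 1.282)² / 0.01 = 394.03, so 395 per arm.

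**2. Effect of strata on the variance.** The unstratified test uses p(1−p) = 0.1875 at the overall 75%. With balance within strata, the true variance uses the mean of p(1−p) over strata. For an 85%/65% split this is (0.1275 + 0.2275)/2 = 0.1775. The variance ratio is 0.1775/0.1875 = 0.947, and the true SE is √(2 × 0.1775/90) = 0.0628.

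**3. Level, 85%/65% split.**
- With the equal-rates variance: Φ(−1.96 × √(0.1875/0.1775)) = Φ(−2.01) = 2.2%.
- At the non-inferiority boundary, placebo strata of 85%/65% become 95%/75% on varenicline. The unstratified sum is 0.75 × 0.25 + 0.85 × 0.15 = 0.315. The within-stratum sum is 0.1775 + (0.0475 + 0.1875)/2 = 0.295. Level = Φ(−1.96 × √(0.315/0.295)) = Φ(−2.03) = 2.1%.
- Simulation (200,000 runs) also gives 2.1%.

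**4. Power, no true difference.** Unstratified: Φ((0.10 − 1.96 × 0.0645)/0.0628) = 33.6%. Stratified: Φ(0.10/0.0628 − 1.96) = 35.7%. The table gives simulated values for several splits by one factor (200,000 runs, 90 per arm; the stratified test here is a score test weighted by stratum size).

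| Assumed AE rates by one factor | Power, unstratified | Power, stratified | Level, unstratified |
|---|---|---|---|
| 75% / 75% | 34.0% | 34.0% | 2.4% |
| 80% / 70% | 34.0% | 34.2% | 2.4% |
| 85% / 65% | 33.5% | 34.9% | 2.1% |
| 90% / 60% | 33.0% | 36.8% | 1.7% |

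The normal approximation is a little more generous at the widest split: with mean p(1−p) = 0.165 it gives 33.1% against 37.9%. The 90%/60% row is also an edge case, because its boundary puts one varenicline stratum at 100%.

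**5. The specific replacement test.** A Miettinen-Nurminen score test with Mantel-Haenszel weights was simulated in the same way. With no stratum difference, power is 34.0% for both tests and both levels are 2.5%. With 85%/65%, power is 35.1% against 33.6%, and level 2.5% against 2.1%. With four unequal strata of 35, 25, 20 and 10 per arm (rates 85/85/65/65%), power is 37.8% against 36.0%, and level 2.4% against 2.1%.

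**6. Without balance within strata.** Simulating the 85%/65% case with unblocked assignment inside strata gives an unstratified level of 2.48%, essentially nominal.

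**The case against.** The case against is substantial, and most of it stands as a limit on the point.

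- A reader might infer that the standard error is simply too large and that power is certainly lost. The documents do not support this. They give no AE rate by stratum, and with equal rates the two tests agree. Every split used above is an assumption.
- The below-nominal level depends on arms being balanced within strata. The protocol says that randomisation is stratified but not how balance is achieved, and step 6 shows the effect vanishing without blocking.
- More extreme splits give more striking figures. With strata at 95/80/70/55% the equal-rates formula gives a level of 1.9%. That is not a level at the non-inferiority boundary, since a constant 10-point excess would put one stratum at 105%.
- The absence of stratification is inferred from silence. The plan also explores smoking status and gender as moderators of outcomes, although that does not define the Aim 2 test.
- Any error is in the cautious direction: non-inferiority becomes harder to declare, not easier.

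What remains is that the plan's one named safety test does not use the factors that define its randomisation, while its efficacy models do. The stratified version costs essentially nothing when the strata are irrelevant.

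**Conclusion.** The point holds as a small, conditional improvement. If AE risk differs by smoking status or gender, and arms are balanced within strata, the unstratified test runs at about 2.1% to 2.2% instead of 2.5% for an 85%/65% split. It gives up roughly 0 to 4 points of power across the splits simulated. If AE risk is the same in all strata, nothing is lost. The test stays valid throughout.

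Two further inferences are not supported. First, stratifying does not rescue the power claim: power stays below 40% in every case computed here. To reach 90% with 180 participants, p(1−p) within strata would have to fall to about 0.043, so the strata would have to explain about 77% of the outcome variance (1 − 0.043/0.1875). The gap between 34% and the stated 90% is a separate matter that needs its own correction. Second, nothing here shows harm from leaving the strata out of the Cox model for days retained, so no change is asked for there.

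**What to change.** In the Specific Aim 2 text, replace the plain test with a stratified one, for example: the AE risk difference (varenicline minus placebo) will be tested with a Miettinen-Nurminen stratified score test using Mantel-Haenszel weights, over the smoking-status-by-gender strata as randomised, with the 10-point margin and alpha unchanged. Add a pooling rule for sparse strata, stated in advance, such as merging over gender within smoking status when a stratum falls below a set count. The documents give no expected smoking or gender mix, so the rule should not assume equal strata. State how the arms are balanced within strata, to the extent that this can be disclosed without weakening concealment.

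The cost is wording in the analysis plan. The change adds no participants, data or visits. It should be made before unblinding, so that the choice between stratified and unstratified limits cannot settle a borderline result. The power statement should be corrected separately.

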### **Statistical Analysis**

**Data Management Plan.** All data will be entered into a standard software package (REDCap). Macro programs will be written to check the data for logical consistency and values out of possible range. Quarterly database management and data integrity audits will be conducted.

**Baseline Analysis.** Categorical clinical and demographic variables will be assessed for balance between groups with chi-square tests of independence, while continuous variables will be assessed using Student's *t*-test. In addition to baseline group differences, preliminary analysis of baseline characteristics with cannabis use outcomes of interest will examine significant correlates of use reduction and abstinence. Characteristics found to be significantly associated with cannabis use outcomes will be included as covariates in the initial stages of adjusted statistical model development.

**Primary Analysis.** The primary aims for the UH3 portion of the protocol are to test the efficacy and safety of varenicline for CUD during a 12-week placebo-controlled trial. **Specific Aim 1:** The primary efficacy outcome is cannabis use reduction as measured by daily substance use logs and examined as the total number of use sessions at each weekly visit (primary interest weeks 6-12). Group differences in reported session use will be examined utilizing a generalized mixed effects models using a log-linear framework for count data. A Poisson distribution will be assumed with a logarithm link function will be used to assess the effects of varenicline treatment, time, and the appropriate interaction. Overdispersion in discrete count models can have a significant

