**Exploratory Analysis.** **Exploratory Aim 1:** Negative affect will be measured weekly during study treatment and compared between groups using generalized linear mixed effects regression models. Model based means will be used to construct the pairwise comparisons between groups and treatment by time interactions will be included to assess differential response over time. **Exploratory Aim 2:** Further, we will assess the time varying relationship between changes in negative affect and cannabis use sessions. Cross lagged panel models will be used to assess the lagged effect of changes in negative affect on cannabis use and visa-versa. Models will also include the autoregressive and synchronous relationships between these variables over time. Models will evaluate the influence of study treatment and medication adherence on the relationship between negative affect and cannabis use through the inclusion of time variable and time invariate effects. If significant treatment effects exist, additional stratified analysis will be conducted to elucidate the magnitude and direction of the effect.

**Additional Data Analysis.** Logistic regression models will be used to assess end of study abstinence (7 day point prevalence abstinence at week 12 and continuous abstinence from week 6 to 12); primary analysis models will be reported both as design adjusted results as well as adjusted for significant clinical covariates. To comprehensively examine the longitudinal efficacy of varenicline, weekly cannabis abstinence will also be analyzed over the entire treatment course using generalized linear mixed effects regression models under a GEE framework. Between study visit cannabis use will be based on daily substance use diaries confirmed via Time-Line Follow-Back procedures. The number of treatment visits attended will be compared between groups using Poisson regression models, while the number of days retained will be assessed using Cox Proportional Hazards regression models. Medication adherence (REDCap video capture of medication-taking; pill counts), tobacco smoking status, and gender will be explored as potential moderators of study outcomes through model interactions. Craving and withdrawal from cannabis will be assessed between groups over time using generalized linear mixed effects models.

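### The mixed models for negative affect, craving and withdrawal do not specify the outcome's own pre-treatment value, which gives up precision and protection against chance baseline imbalance

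*Combined protocol and SAP*

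**What the plan says.** All references are to the combined protocol and SAP.

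- **Hypothesis.** Under the Exploratory Aim, Exploratory Hypothesis 1 is that varenicline, compared with placebo, "for CUD will yield reduction in negative affect".
- **Negative affect.** Statistical Analysis, Exploratory Analysis: "Negative affect will be measured weekly during study treatment and compared between groups using generalized linear mixed effects regression models". It adds that "treatment by time interactions will be included to assess differential response over time". No covariates are listed.
- **Craving and withdrawal.** Statistical Analysis, Additional Data Analysis: "Craving and withdrawal from cannabis will be assessed between groups over time using generalized linear mixed effects models". Again no covariates are listed.
- **Fixed covariates.** The one list is in the Specific Aim 1 text: "All design adjusted models will include baseline average use sessions, study visit, treatment group assignment and randomization stratification variables", namely smoking status and gender.
- **Data-driven covariates.** Baseline Analysis: "Characteristics found to be significantly associated with cannabis use outcomes will be included as covariates in the initial stages of adjusted statistical model development".
- **Data collected.** Table 6 schedules the MCQ (craving), the Cannabis Withdrawal Scale and PROMIS-29. No instrument is identified as the measure of negative affect.

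**The concern.** The hypothesis concerns a reduction, yet the model is described on values collected during treatment and the plan does not say how the starting value enters. For a symptom score measured repeatedly in the same person, the pre-treatment score is an obvious covariate. Leaving it out widens the confidence interval for the arm difference and lets a chance difference at baseline show up, in proportion to the correlation, in the on-treatment comparison. Randomisation is stratified on tobacco smoking and gender, so it does not specifically balance negative affect, craving or withdrawal.

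There is also a question of discretion. Baseline Analysis provides for between-group tests of baseline variables. If such a test shows an imbalance in craving, say, the team would have to decide after seeing data whether to adjust for it. Specifying the term in advance removes that choice.

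**Working it through.** **1. Does any route in the plan bring in the outcome's own baseline?**

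| Route | Baseline outcome it brings in |
|---|---|
| Exploratory Aim 1 model text | None named |
| Craving and withdrawal model text | None named |
| Fixed list under Specific Aim 1 | Baseline use sessions only |
| Data-driven selection (Baseline Analysis) | Whatever is associated with cannabis use outcomes |

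No route does so by design. A baseline craving score could enter through the last one only if it happened to be associated with cannabis use.

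**2. Are the pre-treatment values collected?** Table 6 has 15 columns: screening, baseline, weeks 1 to 12 and one follow-up. After baseline there are 12 + 1 = 13. The table is broken in the available text, but the MCQ and CWS rows each carry 14 marks, so at least 14 − 13 = 1 must fall before treatment. PROMIS-29 carries four marks, the first apparently pre-treatment, whereas Exploratory Aim 1 calls for weekly measurement.

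**3. Is there a figure in the plan to reproduce?** Not for these outcomes: no effect size, power or sample size is given for them. The stated 57 per arm concerns cannabis use. It can be reproduced as 62.79 × 0.8926 = 56.05, rounded up to 57, if the 0.95 correlation is taken as AR(1) over seven weekly visits, a structure the plan does not state. It has no bearing on this point.

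**4. Size of the precision loss.** Inputs: about 90 per arm, and 90 × 0.65 = 58.5, taken as 58, after the 35% attrition allowed for (both from Power and Sample Size). The correlation r between the baseline and on-treatment outcome is an assumption, 0.4 to 0.7. Outcome SD is 1, there is one on-treatment contrast, and there are no other covariates.

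- Relative variance with the own baseline as covariate: f = 1 − r², against 1 without it.
- Detectable difference at 80% power, two-sided 5%: (1.960 + 0.842) × √(2f/n).
- Power for an illustrative difference of 0.4 SD: Φ(0.4/√(2f/n) − 1.96).

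| r | f | Equivalent sample, 1/f | Detectable, 90 per arm | Detectable, 58 per arm | Power for 0.4 SD, 90 per arm |
|---|---|---|---|---|---|
| Unadjusted | 1.00 | 1.00 | 0.418 SD | 0.520 SD | 76.5% |
| 0.4 | 0.84 | 1.19 | 0.383 SD | 0.477 SD | 83.3% |
| 0.5 | 0.75 | 1.33 | 0.362 SD | 0.451 SD | 87.3% |
| 0.6 | 0.64 | 1.56 | 0.334 SD | 0.416 SD | 91.8% |
| 0.7 | 0.51 | 1.96 | 0.298 SD | 0.372 SD | 96.4% |

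**5. Chance imbalance.** The SD of the baseline mean difference is √(2/n): 0.149 at 90 per arm and 0.186 at 58. The 95% ranges are ±1.96 × 0.149 = ±0.29 SD and ±1.96 × 0.186 = ±0.36 SD. An imbalance at those limits shifts the unadjusted on-treatment difference by r times its size: at r = 0.6, about 0.18 SD and 0.22 SD.

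**6. Is the unadjusted comparison biased?** In 4,000 simulated trials with no true effect, 90 per arm, at each of r = 0.3, 0.5 and 0.7, the mean estimate was within 0.007 SD of zero for the on-treatment-only, baseline-adjusted and change-score analyses alike. The SD of the estimate was 0.151 unadjusted against 0.131 adjusted at r = 0.5, and 0.150 against 0.105 at r = 0.7. The difference is in precision, not in bias.

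**The case against.** The strongest reply is that the plan is silent here, and that silence should not be read as a decision. A reader might infer three stronger things, none of which the documents support.

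- **That these models adjust for baseline cannabis sessions instead of their own baseline.** The list does begin with all design-adjusted models, but it sits among sentences about session counts under Specific Aim 1. In Additional Data Analysis the term recurs only with the abstinence analyses, where "models will be reported both as design adjusted results as well as adjusted for significant clinical covariates". Its reach to negative affect, craving and withdrawal is an inference.
- **That the hypothesis is tested with no reference to the starting level.** A mixed model with the baseline visit among the responses and a treatment-by-time term would test differential change, and nothing rules this out. For craving and withdrawal the text is not even limited to on-treatment values. This stands, with one qualification. If the arms are allowed separate baseline means, the contrast at one visit is a change score with relative variance 2(1 − r): 1.2 at r = 0.4 and 0.6 at r = 0.7. That exceeds 1 − r² by (1 − r)², so the form needs stating even on this reading.
- **That the comparison is invalid.** Under randomisation the expected difference in level equals the expected difference in change, and chance imbalance is already reflected in the standard error.

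Two further points stand. The 1 − r² figures compare with no adjustment at all; if sessions, smoking status and gender are already in the model, the gain depends on a partial correlation that cannot be had from the documents. And these outcomes are exploratory or additional and unpowered, so less detail is to be expected.

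**Conclusion.** The point holds as a gap in specification with a real but limited cost. The plan does not provide for the outcome's own pre-treatment value in the models for negative affect, craving or withdrawal. The randomised comparison remains unbiased. What is lost is precision, illustratively 16% to 49% of the unadjusted variance, and protection against chance imbalance of up to about ±0.29 SD at 90 per arm (±0.36 SD at 58) in 95% of trials. The variance figures rest on an assumed r of 0.4 to 0.7 and on no other covariates; the imbalance range rests only on the arm size. Neither the primary efficacy analysis nor the safety analysis is affected.

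That the needed data are already scheduled is secure for craving and withdrawal. It is not secure for negative affect, whose instrument is unnamed: PROMIS-29 covers anxiety and depression, but the plan does not link it to negative affect and its four assessments do not match weekly measurement.

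**What to change.** In Additional Data Analysis, state that the craving (MCQ) and withdrawal (CWS) models each include the pre-treatment value of that same outcome as a covariate, or place the baseline visit in the response vector with a baseline mean common to both arms. Either form should carry visit, arm, arm-by-visit and the stratification variables. The reported result should be the baseline-adjusted mean difference with its confidence interval. Say which pre-treatment assessment is used if there is more than one. Baseline use sessions can remain the baseline term for the cannabis use outcomes.

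In Exploratory Analysis, first name the negative-affect instrument and reconcile its schedule with the weekly measurement described, then apply the same model statement.

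For craving and withdrawal this costs a sentence of wording and no new data. For negative affect the cost depends on the instrument: nothing further if a scheduled measure is chosen and the weekly wording corrected, but added assessments if weekly measurement is kept with an instrument not collected weekly. Both changes should be made before unblinding.
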